To ensure data quality, training sessions will be provided to all research personnel involved in the trial. Standardized case report forms will be created in REDCap for collecting outcome data, with real-time checks for validity and completeness. To maximize usability and minimize missing data, the eCRF will use branching logic. To minimize missing data, the eCRF cannot be submitted with missing data. Coordinating centre personnel will perform quality checks on all data as it is received to screen for and verify potentially erroneous data (e.g., outliers) and review monthly reports of data quality and completeness. To ensure we capture all eligible patients during the enrollment window, we have included investigators from anesthesia and critical care at each study centre, and each day, we will record reason for exclusion for every patient in the ICU and undergoing general anesthesia who is not included in the study.

Data will be stored in a password-protected, encrypted, database on UHN's validated REDCap server. All patients will be identified in the database by a unique study ID. Identifying information will be encrypted and stored in a separate database.

OUTCOME MEASURES

Primary Outcomes

The *primary outcome* will be the occurrence of at least one of the following (composite outcome) occurring within 60 minutes after the end of extubation:

- Severe hypoxemia (oxygen saturation as measured by pulse oximetry falls below SpO2 < 80% for > 5 minutes)
- ii. Cardiac arrest
- iii. Need for airway management (reintubation, insertion of a supraglottic airway, bag-mask ventilation).

Secondary Outcomes

Secondary outcomes will include the new occurrence of the following complications within 60 minutes of extubation:

- i) Difficult airway (i.e., experienced difficulty by an experienced airway manager with any or all of laryngoscopy or tracheal intubation, supraglottic airway use, face-mask ventilation, or front-of-neck airway) and complications related to airway management (e.g., esophageal intubation) if reintubation is required,
- ii) Planned and unplanned non-invasive respiratory support or high flow nasal cannula
- iii) Emergency front of neck airway
- iv) Cardiac arrhythmia requiring chemical or electrical treatment
- v) Severe hypotension (systolic arterial pressure < 65 mmHg recorded at any time or systolic arterial pressure < 90 mmHg for > 30 minutes or new need/increase of vasopressor and/or fluid load > 15 mL/kg)

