- vi) Severe hypertension (systolic blood pressure ≥180 mmHg and/or diastolic blood pressure ≥120 mmHg),
- vii) Aspiration of gastric contents (gastric contents inhaled into the larynx and the respiratory tract),
- viii) Pneumothorax/pneumo-mediastinum,
- ix) Dental injury (notable change to the patient's dentition attributable to extubation or to reintubation, should this be required),
- x) Airways injury (e.g., vocal cord damage, arytenoid dislocation).

We will also collect the following outcomes:

- xi) In-hospital mortality within 7 days after extubation
- xii) Re-intubation within 48 hours of extubation

STATISTICAL ANALYSIS

Sample Size and Number of Study Centres

The sample size calculation is based on the primary objective (to estimate the incidence of immediate complications related to extubation in adult patients after general anesthesia and/or after critical illness). Based on estimates from current literature, ⁶⁻⁸ we expect an incidence of such complications around 8% (80 per 1,000 patients). Assuming such incidence, 2,827 patients need to be included to estimate a 95% confidence interval not wider than 2% (20 per 1,000 patients). Assuming approximately 5% of patients will be missing primary outcome data, we aim to collect data on 3,000 patients to meet our target sample size of 2,827. This sample size will also allow the inclusion of 15-22 candidate factors in the secondary objectives (i.e., investigation of the risk factors for the occurrence of the primary outcome).

Since we aim to estimate the overall incidence of the primary outcome in the population of interest (rather than the expected incidence in a centre), all eligible patients could be included during the enrollment window without any limitations on the number of enrolled patients in each centre. We estimate we will need to recruit at least 60 centres to achieve the target sample size, assuming an average of 50 extubation procedures in each centre in the

enrollment window. If the number of extubations per centre is lower than anticipated, we will continue to recruit centres until we reach our target sample size.

Interim Analysis

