We plan an interim analysis with the data from the first 10 centres to complete their enrollment window to check if the magnitude of the primary outcome is broadly in line with the expected incidence. If the real incidence is different than expected incidence, or if we observe marked difference between populations in the OR and in the ICU, the sample size calculation may be updated, and the number and type of participating centres may be increased and diversified as needed. As this is an observational study, the interim analysis will not drive decisions about stopping for harm or futility.

Statistical Analysis

Descriptive statistics will be used to describe the patient characteristics. Continuous data will be expressed as mean and standard deviation or median and interquartile range, and categorical data as number and percentage. Bivariable analyses will be conducted using $\chi 2$ or Fisher exact test for categorical variables, and the Mann-Whitney or t test for continuous variables. A complete case analysis (with no assumptions made for missing data) will be performed. For the primary objective, the incidence of primary and secondary outcome measures (with 95% confidence interval) will be estimated overall, and within clinically relevant strata (e.g., sex, age, extubation in OR vs. ICU, low vs. high-risk extubation, global region, comorbidities, indication for intubation, complications at the time of original intubation, etc.).

For secondary objectives, (1) to identify risk factors for post-extubation complications, multivariable models (which may include logistic regression, Poisson regression, negative binomial regression, according to the nature of the data) adjusting for patient and surgical characteristics will be conducted. (2) Kaplan-Meier curves and Cox regression may be implemented to analyze survival data, if appropriate. (3) Exploratory analysis will be conducted to understand the current practice related to extubation and adherence. Given the multicentre enrollment, all analyses will be performed using multi-level models (with patients nested within study centre). All tests will be 2-sided and a p-value less than 0.05 will be considered statistically significant. Statistical analysis will be performed using R software (R Foundation for Statistical Computing, Vienna, Austria).

REFERENCES

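### Secondary outcome ii counts planned non-invasive support or high-flow nasal cannula as a new complication, so its incidence mixes preventive practice with harm

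*Protocol*

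**What the plan says.** In the protocol's Outcome Measures, the list under Secondary Outcomes opens: "Secondary outcomes will include the new occurrence of the following complications within 60 minutes of extubation". Item ii of that list is "Planned and unplanned non-invasive respiratory support or high flow nasal cannula". The protocol does not say that the planned and unplanned parts will be reported apart.

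The Statistical Analysis section states that "the incidence of primary and secondary outcome measures (with 95% confidence interval) will be estimated overall, and within clinically relevant strata". The strata it gives as examples include location (OR or ICU) and the risk level of the extubation. The same section foresees an exploratory description of current extubation practice.

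On the smaller point, the third component of the primary composite is "Need for airway management (reintubation, insertion of a supraglottic airway, bag-mask ventilation". Secondary outcome iii is "Emergency front of neck airway". Secondary outcome i, in defining a difficult airway, names "laryngoscopy or tracheal intubation, supraglottic airway use, face-mask ventilation, or front-of-neck airway" together.

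**The concern.** A patient who goes onto high-flow oxygen straight after extubation because the team decided so in advance has not had a new adverse event. Under item ii that patient is counted as having a complication, which contradicts the list's own lead-in.

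At stake is the meaning of one reported result. Clinicians are likely to plan support more often in patients they judge to be at high risk, and in the ICU. These are the strata in which the incidence of item ii will be shown, so a difference between them could reflect prior judgement as much as harm. The protocol's Rationale says that baseline complication rates are needed to evaluate later interventions and guidelines. A baseline that rises whenever preventive support is used more often, whatever happens to patients, serves that purpose badly.

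A second, minor inconsistency sits beside it. The airway component of the primary composite does not name emergency front-of-neck airway, although secondary outcome i groups that technique with the ones the component does name.

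**Working it through.** **Inputs from the protocol.** Expected primary incidence 8%; full 95% confidence interval width 2%; required number 2,827; planned enrolment 3,000, allowing for about 5% missing primary outcome data.

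**Inputs not in the protocol (assumptions).** Planned support *a* = 2% to 10%; unplanned support *u* = 2% to 5%; patients with an emergency front-of-neck airway who meet no other primary component, *f* = 0.01% to 0.2%.

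**1. The plan's own figure.** The Wald interval for one proportion gives n = 4z²p(1−p)/w² = 4 × 1.96² × 0.08 × 0.92 / 0.02² ≈ 2,827. The stated number reproduces. Item ii is not part of the primary composite, so nothing in step 2 touches this figure.

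**2. Share of item ii that is planned, a/(a+u).**

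| Planned | Unplanned | Counted under item ii | Share planned |
|---|---|---|---|
| 2% | 5% | 7% | 29% |
| 2% | 2% | 4% | 50% |
| 5% | 5% | 10% | 50% |
| 10% | 5% | 15% | 67% |
| 5% | 2% | 7% | 71% |
| 10% | 2% | 12% | 83% |

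Two comparisons from this table show the effect on strata:

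- *Same harm, different practice.* Take two strata, each with 5% unplanned support, one with 2% planned and the other with 10%. They would read 7% and 15%, a ratio of 15/7 ≈ 2.1, with no difference in unplanned events.
- *Order reversed.* A stratum with 10% planned and 2% unplanned reads 12%. One with 2% planned and 5% unplanned reads 7%. The stratum with fewer unplanned events looks worse.

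**3. Front-of-neck airway in the primary composite.** Adding *f* to 8% gives 8.01% to 8.20%.

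- Extra events in 2,827 patients: 2,827 × 0.0001 ≈ 0.3, up to 2,827 × 0.002 ≈ 5.7.
- Interval width at n = 2,827: 2.001% to 2.023%.
- Number needed for a 2% width: 2,831 to 2,892. The like-for-like comparison is with the patients expected to have outcome data, 3,000 × 0.95 = 2,850. At the upper extreme, 2,850 patients give a width of 2 × 1.96 × √(0.082 × 0.918 / 2,850) ≈ 2.01%.

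**The case against.** The strongest reply is that item ii names both categories, so the authors evidently recognise the distinction. Separate reporting is commonly settled in a statistical analysis plan, which is not shown, and the case report form may already hold the two apart. Counting all support also avoids relying on a clinician's label, which may be applied after the fact. The label point stands as a cost of the remedy. The rest does not remove the problem: the protocol defines the pooled item as a complication and plans an incidence for it.

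Four stronger readings are tempting, but the documents do not support them:

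- *That differences between centres in planned use would dominate the comparisons.* No rates are given, no between-centre comparison of item ii is planned, and the analyses nest patients within centre.
- *That the risk-factor results are compromised.* The sample size section ties that objective to the primary outcome. The Statistical Analysis section speaks more broadly of post-extubation complications, but it specifies no model for item ii.
- *That the case report form lacks a planned/unplanned field.* The form is not shown.
- *That the composite ranks severity inconsistently.* It is met by any one component, without rank or weight, so there is no ordering to breach.

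On front-of-neck airway, it can fairly be said that the event falls within the general phrase that heads the component, that most such patients would probably meet another component, and that the event is reported anyway as secondary outcome iii. All of this has force and is why the point is minor. What remains is that the parenthesis has no marker of being illustrative, whereas secondary outcomes i and x use one.

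**Conclusion.** The concern holds for secondary outcome ii. As written, intended support is counted as a complication, and both the overall incidence of that item and its strata by location and risk level would mix practice with harm. How much is unknown: the 29% to 83% range and the reversed ordering rest wholly on assumed rates and show only that the effect could be large. The consequence is confined to this one secondary outcome. The primary incidence, the sample size and the interim check do not depend on it.

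The omission of front-of-neck airway from the primary airway component is a real mismatch between two lists, but a matter of clarity. Under the assumed range it moves the primary incidence by at most 0.2 percentage points and leaves the precision target practically intact.

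**What to change.** 1. Define secondary outcome ii as unplanned initiation or unplanned escalation of non-invasive support or high-flow nasal cannula within 60 minutes of extubation.
2. Report planned support separately, in the description of current practice that the Statistical Analysis section already foresees. Also tabulate planned and unplanned together, so that comparison with sources that pool them remains possible.
3. Record whether support is planned before the extubation takes place. This limits the one real drawback, reliance on a label that could otherwise be assigned with hindsight.
4. Do not add planned support to the risk-factor models as a default covariate. It is chosen because of perceived risk and delivered inside the outcome window, so its coefficient would be hard to interpret.
5. As a minor edit, name emergency front-of-neck airway in the third component of the primary composite, matching secondary outcome i, and keep it as a separately reported secondary outcome.

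The cost is two wording changes and, only if the form does not already have it, one field. The field matters for timing: pooled records cannot reliably be split afterwards, so centres that have already enrolled without it could report only the total.

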Despite the frequency of extubation and the potential for life-threatening complications of extubation failure, we currently lack systematic data on the rate and circumstances under which these severe complications occur.³ The limited data on complication rates indicate 10-30% of extubations may lead to severe complications, depending on the population and outcome definition.^{5,10-16} However, the certainty of these estimates is severely limited because they are based on studies that are small,¹¹ mostly single-centre, based on clinician recall,^{5,10} only capture a small portion of extubation complications,¹⁴ or do not reflect current clinical practice.¹² Beyond these data, extubation complications and practices have not been thoroughly studied.⁴ Yet extubation management decisions and outcomes depend on a complex interplay of patient and situational characteristics,⁴ so a large, systematic study would be required to make conclusions about the best extubation technique in various patient populations and settings.¹⁷

Historically, extubation has received significantly less research attention than intubation¹⁷⁻²⁰ (i.e., the process of inserting the endotracheal tube at the start of mechanical ventilation), even though complications at extubation may occur as frequently as complications at intubation, but may have increased risk of severe patient harm.^{6-8,12,18,21-25}

Promisingly, a recent focus on intubation complications, risk factors, and best-practices has decreased intubation related complications 26 – an evidence-based bundle of intubation strategies decreased airway complications by $26\%^{27}$ – suggesting that a similar program of research focusing on extubation could have a comparable impact on patient safety and outcomes. 28

As a result, there have been calls for research to identify risks of extubation complications and effective extubation techniques.^{5,7,19,20,28-30} In particular, high quality baseline data on complication rates are needed to evaluate future interventions and clinical practice

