To meet our target sample size (n=3,000), we have established a network of at least 60 broadly representative academic and non-academic hospitals worldwide that will report on patient data for this study. We will collect information about each study centre at the time of enrollment (e.g., community vs academic hospital, unit type [ICU, post-anesthesia care unit], number of beds in the hospital, number of beds in the unit). Each centre will be assigned a two-week enrollment window between January 2025 to December 2026, during which they will collect data on all eligible patients up to a maximum of 50 patients per centre.

Any future collaborations and transfer of data from/to UHN will be submitted for Research Ethics Board (REB) review via future amendment submission.

Patients

All potentially eligible patients will be identified by local investigators by screening all inhospital extubations occurring in the ORs, out of OR anesthesia locations and ICUs during the enrollment window. Potentially eligible patients undergoing general anesthesia will be identified by screening daily preoperative assessment clinic lists, operating room booking lists, incoming patient lists on surgical wards, and monitoring operating room and out of OR procedure lists for add-on surgeries cases. Potentially eligible patients in the ICU will be identified by screening ICU census lists.

Inclusion Criteria

All adult patients (≥18 years old) undergoing extubation of an endotracheal tube (including index extubation and re-extubations) after general anesthesia in the OR, out of OR anesthesia location or ICU during the specified enrollment window will be included.

Exclusion Criteria

Patients will be excluded if the extubation is:

- (i) performed in the context of withdrawal of life support measures or
- (ii) performed for tracheostomy decannulation.

For each patient who is not included, reasons for exclusion will be reported.

Ethical Considerations

The study will be conducted in accordance with Good Clinical Practice guidelines³⁵ and the Declaration of Helsinki.³⁶ Additionally, the research will be conducted in compliance with local REB requirements at each centre.

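### The 2-point confidence interval width quoted for 2,827 patients assumes independent patients, so with about 60 centres and 8% incidence it holds only if the ICC is essentially zero

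*Protocol*

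**What the plan says.** In the Protocol, under Sample Size and Number of Study Centres, the planning value is "we expect an incidence of such complications around 8% (80 per 1,000 patients", and on that basis "2,827 patients need to be included to estimate a 95% confidence interval not wider than 2% (20 per 1,000 patients". The only inflation is for missing outcomes: "Assuming approximately 5% of patients will be missing primary outcome data, we aim to collect data on 3,000 patients". The same section turns this into centres: "We estimate we will need to recruit at least 60 centres to achieve the target sample size". The mean yield it takes per centre is 50 extubations over the enrolment window. It adds that the target is the overall incidence in the population of interest and not the incidence in a single centre, and uses this to argue that no limit per centre is needed. The section mentions no ICC, design effect or between-centre variance.

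Under Statistical Analysis, the protocol says that "all analyses will be performed using multi-level models (with patients nested within study centre". Under Interim Analysis, data from the first 10 centres may lead to a revised sample size. The stated triggers are an incidence different from the expected one, or a marked difference between operating room and ICU patients.

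**The concern.** The study is sized under one variance model and analysed under another. The sizing treats every patient as an independent draw. The analysis recognises that patients in one hospital share case mix, staff and practice, and so tend to have similar outcomes. If true incidence differs between hospitals, 2,827 patients in about 60 clusters carry less information than 2,827 independent patients, and the interval is wider than stated.

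Estimating incidence is the primary objective, and the 2-point width is the figure on which 2,827 rests. A reader of the protocol, or of a report that cites it, would take that width as a property of the design. As written, it depends on an assumption that is neither stated nor supported.

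**Working it through.** **Inputs.** From Sample Size and Number of Study Centres: incidence p = 0.08, full width 0.02 (half-width h = 0.01), 2,827 evaluable patients, 3,000 enrolled, 60 centres. The ICC is not in the protocol and is assumed over a range.

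**Step 1: reproduce the stated figure.** The Wald formula for independent observations is n = 1.96² × p(1 − p) / h² = 3.8416 × 0.0736 / 0.0001 = 2,827.4. This matches 2,827, so the design effect used is 1.00. For missing data, 2,827 / 0.95 = 2,976, rounded to 3,000. The arithmetic is right for a simple random sample.

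**Step 2: add the clustering.** Evaluable patients per centre: m = 2,827 / 60 = 47.1. Design effect: DE = 1 + (m − 1) × ICC. Full width = 2 × 1.96 × √(0.0736 × DE / 2,827). Effective sample size = 2,827 / DE. The between-centre SD of true incidence that corresponds to a given ICC is √(ICC × 0.0736).

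| Assumed ICC | Between-centre SD (points) | DE | Full width (points) | Effective n |
|---|---|---|---|---|
| 0 | 0 | 1.00 | 2.00 | 2,827 |
| 0.001 | 0.9 | 1.05 | 2.05 | 2,702 |
| 0.005 | 1.9 | 1.23 | 2.22 | 2,297 |
| 0.01 | 2.7 | 1.46 | 2.42 | 1,935 |
| 0.02 | 3.8 | 1.92 | 2.77 | 1,471 |
| 0.05 | 6.1 | 3.31 | 3.64 | 855 |

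The formula takes centres as equal in size. That fits the Study Centres section, which enrols "up to a maximum of 50 patients per centre". Using m = 50 changes little: 2.44 points at ICC 0.01 and 3.72 at 0.05.

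**Step 3: is there slack?** Suppose all 3,000 patients were evaluable. The independent-patient width would be 1.94 points, and the design effect that brings it back to 2 points is 3,000 / 2,827.3 = 1.061. With 50 per centre, the tolerable ICC is 0.061 / 49, or about 0.0012. That is a between-centre SD of about 1 point around 8%.

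**The case against.** The strongest defence is that the sample size section aims at the overall incidence and not at centre-level incidence. This does not remove the problem. The inference is to a wider population of which the participating hospitals are a sample, so variation between hospitals is part of the error in the overall estimate.

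Several other points stand and limit the finding:

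- The planned analysis already models centre. The concern is therefore a forecast that is too favourable, not bias or under-coverage in the reported interval.
- No ICC is given, so the size of the shortfall is assumed. A very small ICC costs little: 2.05 points at 0.001. Nothing in the protocol singles out 0.05.
- The stated width is conditional on 8%. At a lower incidence there is room: with independent patients the width is 1.75 points at 6% and 1.61 at 5%. This allows design effects of 0.0736 / 0.0564 = 1.30 and 0.0736 / 0.0475 = 1.55 within 2 points.
- Sixty centres is a minimum. With 2,827 patients over 100 centres, m = 28.3 and, at ICC 0.01, DE = 1.27 and the width is 2.26 points. That reduces the shortfall but does not remove it.
- The interim analysis can change the sample size. Its triggers are incidence and the operating room/ICU contrast, however, so an incidence of 8% with heterogeneous centres would give no stated reason to revisit 2,827.

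A reader might also set the Rationale's statement that "10-30% of extubations may lead to severe complications" against the 8% and conclude that the planning incidence is too low. The documents do not support this. The Rationale ties that range to differing populations and outcome definitions and calls its certainty severely limited, and the interim analysis already checks incidence.

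**Conclusion.** The precision statement is wrong as written, because it omits a condition on which it depends. At 8% incidence, 2,827 patients from about 60 centres give a 2-point interval only if the ICC is essentially zero. The protocol's own design does not support a near-zero ICC: it recruits hospitals of different types around the world, mixes operating room and ICU extubations, and allows that those two populations may differ markedly. Over assumed ICCs of 0.001 to 0.05 the width runs from 2.05 to 3.64 points. The direction is certain for any positive ICC; the amount is not.

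Two stronger conclusions are tempting. One is that the 2-point width will definitely be missed. Without an ICC, and with the incidence still unknown, the documents show only that the claim is unsupported at 8%. The other is that precision is the study's sole design criterion, so that the sample size fails altogether. The same section also justifies the size by the 15 to 22 candidate risk factors it would allow, and nothing here shows that 3,000 patients are too few to be useful.

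**What to change.** In Sample Size and Number of Study Centres, keep 2,827 and 3,000 and make the precision conditional. Suggested text: *With 2,827 evaluable patients from 60 centres and 8% incidence, the expected full width of the 95% confidence interval is 2.0 points if patients are independent, and about 2.05, 2.2, 2.4, 2.8 and 3.6 points for assumed intracluster correlations of 0.001, 0.005, 0.01, 0.02 and 0.05.*

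In Interim Analysis, add that any sample-size update will include a design effect over an assumed ICC range. The ICC from the first 10 centres can be reported, but as indicative only. With 10 centres of about 47 patients, the usual large-sample standard error is about 0.015 at a true ICC of 0.01 and 0.019 at 0.02, about as large as the quantity itself. It should not drive an update alone.

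The cost is a few sentences and no added enrolment. The drawback is that the stated precision becomes less favourable.

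### The analysis section calls for multi-level models throughout yet lists tests that ignore centre, and does not tie the primary incidence to the overall population value the protocol targets

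*Protocol*

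**What the plan says.** Three statements in the protocol bear on this point.

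- **Target.** Sample Size and Number of Study Centres says that the study aims to "estimate the overall incidence of the primary outcome in the population of interest (rather than the expected incidence in a centre"). The same section plans for an 8% incidence: "2,827 patients need to be included to estimate a 95% confidence interval not wider than 2% (20 per 1,000 patients").
- **Method.** The last paragraph of Statistical Analysis says that "all analyses will be performed using multi-level models (with patients nested within study centre"). No exception is made. The primary-objective text before it asks for incidences with 95% confidence intervals, overall and by stratum, but names no estimator.
- **Bivariable tests.** The first paragraph of Statistical Analysis assigns chi-square or Fisher tests to categorical variables and "the Mann-Whitney or t test for continuous variables". The section closes with a two-sided 0.05 threshold for all tests.

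**The concern.** There are two problems.

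First, the listed bivariable tests treat patients from one centre as independent. They are not multi-level models, so the section gives two incompatible instructions. Where a factor differs mainly between centres, the unclustered p-value is too small.

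Second, taken literally, the multi-level rule covers the primary objective. For a yes/no outcome the usual multi-level model is a logistic regression with a random intercept for centre. Back-transforming its intercept gives the risk in a centre whose random effect is zero, that is, the median centre. When centres differ and risk is below 50%, this lies below the population risk, and a larger sample does not close the gap. The study's main result is one incidence, planned to within 1 point either way. The protocol should therefore make clear which quantity that incidence is.

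**Working it through.** **Inputs from the protocol:** incidence 8%, total 95% CI width 2 points (half-width 1 point), 2,827 evaluable patients, 5% missing, 3,000 enrolled, at least 60 centres averaging 50 patients. **Assumed:** the between-centre SD *s* on the logit scale and the intracluster correlation (ICC), because the protocol gives neither.

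**Step 1. The protocol's own figure.** For independent patients, n = 1.96² × 0.08 × 0.92 / 0.01² = 2,827. This reproduces. Allowing for missing data, 2,827 / 0.95 = 2,976, which 3,000 covers; 60 × 50 = 3,000.

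**Step 2. Median-centre incidence.** Let the risk in a centre be expit(b + sZ), with Z standard normal. Solve E[expit(b + sZ)] = 0.08 for b by 80-point Gauss-Hermite quadrature; expit(b) is the incidence at random effect zero. The observed-scale ICC is Var[expit(b + sZ)] / (0.08 × 0.92). The design effect is 1 + 49 × ICC, and the clustered half-width is 1.96 × √(0.08 × 0.92 × design effect / 2,827).

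| Assumed SD | Incidence at random effect zero | Shift from 8% (points) | Observed-scale ICC | Design effect | Clustered half-width (points) | Shift / half-width |
|---|---|---|---|---|---|---|
| 0.18 | 7.90% | 0.10 | 0.002 | 1.12 | 1.06 | 0.1 |
| 0.3 | 7.73% | 0.27 | 0.007 | 1.33 | 1.15 | 0.2 |
| 0.5 | 7.27% | 0.73 | 0.019 | 1.94 | 1.39 | 0.5 |
| 0.7 | 6.66% | 1.34 | 0.039 | 2.89 | 1.70 | 0.8 |
| 1.0 | 5.56% | 2.44 | 0.080 | 4.92 | 2.22 | 1.1 |

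The shift equals the planned 1-point half-width at an SD of about 0.6 (6.98%). The clustered half-width is the fairer yardstick, because the variation that produces the shift also widens the interval. Averaging the same fitted model over the distribution of centres returns 8%, provided centre size is unrelated to risk.

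**Step 3. Size of an unclustered test for a factor that is constant within a centre.** Approximate actual size = 2 × [1 − Φ(1.96 / √design effect)], with 50 patients per centre.

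| Assumed observed-scale ICC | Design effect | Actual size of a nominal 5% test |
|---|---|---|
| 0.005 | 1.245 | 7.9% |
| 0.01 | 1.49 | 10.8% |
| 0.02 | 1.98 | 16.4% |
| 0.05 | 3.45 | 29.1% |

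Global region, one of the strata listed in Statistical Analysis, is such a factor. For factors that vary within a centre, such as sex or OR versus ICU, this formula does not apply; the unclustered test can be near nominal or conservative.

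**The case against.** A reader might infer that the protocol is bound to report the wrong quantity and a headline incidence that is too low. The text does not support that. It fixes no link function and no type of prediction for the primary objective. Logistic, Poisson and negative binomial models are named only for the risk-factor objective, and the multi-level sentence closes the paragraph on secondary objectives. A multi-level model can be averaged over centres to recover the population value, and an analysis plan that is not shown may say so.

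A reader might also equate the median centre with the centre-level quantity that the protocol sets aside. They differ: an expected incidence in a centre is naturally a mean over centres. That clause also serves mainly to justify enrolling without a limit per centre, so it is not a full definition of the analysis target. It does still name the overall incidence as the aim, and the median centre is not that.

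The size of the shift depends on an assumption. At low heterogeneity it is only 0.1 to 0.3 point. The protocol does give some reason to expect variation between centres: it mixes OR, out-of-OR and ICU extubations in academic and non-academic hospitals worldwide.

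Finally, the bivariable tests stand next to the descriptive statistics, and inference on risk factors is left to the multivariable models. This lowers the stakes but does not remove the conflict. The protocol applies its 0.05 threshold to all tests, and an analysis plan could not keep these tests, or a simple proportion, without departing from the blanket multi-level rule.

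**Conclusion.** The contradiction within Statistical Analysis is certain and rests on the text alone: the blanket multi-level rule and the listed single-level tests cannot both be applied. The mismatch in the primary incidence is conditional. It arises if the incidence is read at random effect zero, and the protocol neither requires nor excludes that.

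If it is read that way and the population incidence is 8%, the shift is 0.1 to 0.3 point at a centre SD of 0.18 to 0.3, and 0.7 to 2.4 points at an SD of 0.5 to 1.0. The latter range is about 0.5 to 1.1 clustered half-widths. Inflation of the test size, to about 8% at an ICC of 0.005 and 16% at 0.02, concerns mainly factors that vary between centres. All these sizes assume normally distributed centre effects; those using the design effect also assume 50 patients per centre. This point does not show the stated sample size of 2,827 to be wrong: it reproduces under independence.

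The text should be corrected before analysis.

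**What to change.** Amend Statistical Analysis in three places.

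1. State that overall and stratum incidences of the primary and secondary outcomes are population-average estimates. Give them either as the observed proportion with a 95% CI from a centre-robust variance, or as a multi-level estimate averaged over centres.
2. Limit the multi-level sentence to the risk-factor models.
3. Replace the bivariable tests with centre-clustered versions, or label those comparisons descriptive and drop their p-values.

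The cost is analysis wording only. No data collection changes, and standard R packages cover these methods. Confidence intervals will be somewhat wider than under independence.
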